## **E. Potential Scientific Problems and Feasibility:**

[figure not shown]
**Overall feasibility:** While an ambitious study, PI and co-investigators have performed numerous observational studies and clinical trials in youth and adults with T1D (41, 82, 83) and T2D (84), including the NIH TODAY (85, 86), RISE (87), and JDRF studies in T1D youth and adults, including Canadian Study of Longevity in Diabetes (Longevity), Coronary Artery Calcification in Type 1 Diabetes Study (CACTI), and Bromocriptine Quick Release (BCQR) as Adjunct Therapy in Type 1 Diabetes (NCT02544321) with renal measures similar to those now proposed (36, 41, 88-101). The proposed study in this application will be completed in a single research visit, limiting concerns for drop-out and retention. By recruiting adolescents (12-18 y) we expect that 30-50% will have hyperfiltration at baseline per our previous studies in this age group (23, 54, 65, 66, 81, 102-104). Drs. [name] and [name] have extensive experience with MR imaging in youth (73-75, 105-110). Drs. [name], [name] and [name] are experienced in renal physiology measures (38, 55, 60, 62, 64, 79-81). [name] is an international leader in renal MRI BOLD and ASL. Finally, our proposal is based on strong preliminary data (41, 55, 64, 111-113) and a track record of successful collaborations (16, 36, 55, 60, 86, 92, 93, 95, 111, 112, 114-120). We are therefore the ideal group to perform the important research proposed.

**Potential scientific problems:** In any clinical study, unforeseen human factors provide challenges. We have experience with hyperglycemic clamps, iohexol and PAH clearance studies and MRI methods in youth with T2D, and have already obtained preliminary data. Expected outcomes and limitations for each aim are summarized below:

### ***Aim 1 - Expected outcomes and limitations:***

We expect copeptin to be greater in T1D youth with hyperfiltration vs. those without hyperfiltration. In youth with short-standing T1D and hyperfiltration, we anticipate that copeptin concentrations will positively correlate with GFR, ERPF, RVR, glomerular pressure and albumin excretion. We theorize that elevated AVP results in afferent arteriolar vasodilation with resultant increased ERPF and glomerular pressure which leads to hyperfiltration (Fig 10). Furthermore, a mild hyperglycemic clamp allows us to quantify intrarenal hemodynamic function in a glycemic milieu similar to their native pathophysiology. In contrast, a hyperinsulinemic-euglycemic clamp would render the participants completely normoglycemic, which does not reflect their usual glycemic environment, and expose them to high concentrations of insulin which may interfere with the assessment of their intrarenal hemodynamic function. Most studies focus on the classical definition of hyperfiltration which disregards ERPF and  $P_{GLO}$ . Our proposed project addresses these concerns and others in regard to scientific rigor, by also examining hyperfiltration defined as  $FF (GFR/ERPF) > 17.7\%$  and calculating  $P_{GLO}$  by Gomez' equations (67, 121). The sustained hypermetabolism of hyperfiltration is thought to initiate the development of nephropathy as the energy profile of T1D cannot accommodate the increased energy demand which leads to progressive nephron loss (122-127). We hypothesize that the elevated AVP activity in T1D may play a role in initiating hyperfiltration through vasodilation of the afferent arterioles with increased ERPF and glomerular hypertension (Fig 10).

**Fig 10. Proposed Mechanism of Vasopressin Over-activity and Hyperfiltration**

Normal AVP activity at V2R at the afferent arteriole in T1D (a) is associated with normal tone (b), glomerular pressure and GFR. Elevated AVP activity at V2R at the afferent arteriole in T1D (a) leads to vasodilation (b) with increased RBF, increased glomerular pressure and hyperfiltration.

Control for potential confounders influencing intrarenal hemodynamic function includes: renal measures obtained during mild hyperglycemia, macronutrient and salt-controlled diet, limiting strenuous exercise for 3 days prior to visit, and control for stage of menstrual cycle. Our preliminary data demonstrate the feasibility of the proposal in young adults with T1D and our unique ability to perform the highly specialized intrarenal hemodynamic measures.

#### **Aim 2 - Expected outcomes and limitations:**

We expect increased renal perfusion and renal O2 consumption in T1D youth with hyperfiltration. We also anticipate a strong correlation between copeptin, renal perfusion and renal O2. Based on our preliminary work, we expect the 2 renal sequences (BOLD and ALS) to be completed within 60 min. [name] NIH R56, JDRF and ADA studies had adolescents with T1D, T2D and without diabetes undergo similar MRI procedures lasting 120 min, indicating that recruiting and tolerability in youth for such procedures are feasible. Our research MRI is equipped with in-MRI movie-viewing with noise-cancelling headphones and thus is very tolerable to youth. The participant will be monitored by heart rate, blood pressure, and oxygen saturation measurements, and will be able to communicate with the MRI technician and investigator immediately outside of the scanner. As BOLD is potentially influenced by O2 delivery (ERPF) and O2 consumption (tubular Na transport accounts a majority of renal O2 consumption (128)) we will control for ERPF and fractional excretion of sodium (FeNa). We will perform the MRI fasting in the morning to remove the effects of acute glycemic variations on RPF and the impact of changes in hydration status of renal oxygenation. Participants on medications that might alter O2 delivery and/or consumption, e.g. angiotensin-converting enzyme inhibitors (ACE-I), angiotensin receptor blockers (ARBs) and diuretics will be excluded.

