**Table 1: Eligibility Criteria**

Inclusion criteria	Exclusion criteria
Antibody+ T1D with $<10$ yr duration	Severe illness, recent DKA
Age 12-21 years	ACEi, ARB, diuretics, SGLT 2/1 blockers, atypical antipsychotics, steroids
BMI $\geq 5\text{ percentile}$	Macroalbuminuria ( $>300\text{mg/g}$ ) or eGFR $<60\text{ml/min}/1.73\text{m}^2$
Weight $<300$ lbs.	Pregnancy, nursing
HbA1c $<12\%$	Anemia or allergy to shellfish or iodine
BP $< 140/90\text{ mm Hg}$	

intrarenal hemodynamic function. They will also be provided with a 3-day diet instructions (45% carbohydrates, 30% fat, 25% protein and a goal of 3.45 g salt/day), with females studied in the follicular phase of the menstrual cycle where possible to limit impacts of nutrient and menstrual hormone variations on IR and renal function, as previously described (61). Participants will ask to administer their long

acting insulin (e.g. Lantus or Levemir) like they normally would. Patients on insulin pumps can remain on their basal rate throughout the study. If on a hybrid-closed loop (artificial pancreas), participants will be asked to open their loop for the duration of the study. The morning of the study, participants will be asked to check their blood sugar prior to arriving at the CTRC. If their blood sugar is  $\geq 250$  mg/dL, they will be asked to administer a bolus of short acting insulin using their home correction factor with a blood sugar target of 200 mg/dL.

Participants will arrive the evening before, or present fasting in the morning and have 2 IVs placed and have their blood glucose concentrations clamped in the mild hyperglycemic range (details below) (Fig 8). Baseline blood will be drawn for serum copeptin, lipids, insulin, cystatin c, creatinine, sodium, hematocrit and total protein, and iohexol and PAH boluses given via IV (see below for details). GFR and ERPF will be measured by iohexol and PAH clearance in plasma. A 4 hr urine sample will be collected to calculate ACR and AER.

**Specific methods:** Outcomes are summarized in **Table 2**. Detailed methods are listed below:

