**Figure 8 Study Protocol for SA 1**

[figure not shown]

Table 2 – Aims 1 and 2	
Primary Outcomes	Measurement Tool
Copeptin	ThermoFisher Kryptor Plus
GFR	Iohexol clearance
ERPF	PAH clearance
Renal O 2	BOLD-MRI
Renal perf.	ASL-MRI
Secondary Outcomes	
RVR	MAP/RBF (Table 3)
eGFR	Creatinine, cystatin C
Albumin excretion	Albumin-to-creatinine ratio (ACR)

**Hyperglycemic insulin clamp:** One IV will be placed in each arm to clamp the blood glucose concentrations between 170-190 mg/dL. One IV will be used to administer the boluses of iohexol and PAH in addition to a variable infusion of 20% dextrose and insulin, and the other IV will be used for blood draws. Blood glucoses will be measured every 10 minutes at the bedside, and glycemic control will be achieved using the modified and simplified insulin clamp methodology to remove glycemic effects on GFR and ERPF. The rate of insulin is adjusted based on blood specimens drawn every 10 minutes (example algorithm). Patient blood glucose (BG) levels will be checked at 8am, and adjusted to reach and maintain mild hyperglycemia up until 10am. If participant BG <70mg/dl, we will give 4 oz juice and re-test BG in 15 min. If still <70mg/dl, another 4 oz juice will be given, and BG will be re-tested 15 min later. If still <70 mg/dl,

study MD will be called, and IV D20 will be started at 100ml/hr. For BG between 70-180 mg/dL, a variable D20 infusion will be given on a sliding scale based on participant current BG and weight, as used in previous and current studies (COMIRB #13-0122, #16-1752, #18-0704). Once BG  $> 190$ mg/dl, D20 will be discontinued. If BG is not responding to changes within 2 hours or if increases above 200 mg/dl, a study physician will be contacted. Each time blood is drawn during the clamp, blood will be drawn to a clear line in the syringe to ensure there will be no IV fluid dilution and will be re-infused into the subjects after obtaining the blood sample to minimize blood loss. A blood glucose range of 170-190mg/dL (mild

hyperglycemia) was chosen to limit the acute effects of severe hyperglycemia on GFR and ERPF reproducibility, while allowing us to assess renal function in a glycemic milieu similar to the participants native

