-----------------	-----------------	---	---	---

**Abbreviations:** BOLD: Blood oxygen level dependent, SSFP: steady state free precession, VLA: vertical long axis view, LVOT: left-ventricular outflow tract view, GRE: gradient recalled echo.

**Recruitment:** Ultimately 50 youth with T1D (50% male) will be enrolled (see power analysis). Recruitment will begin year 1 and will consist of adolescent patients with type 1 diabetes from the Barbara Davis Center for Childhood Diabetes (BDC), where principal investigator [name] and co-investigator Drs. [name] and [name] are medical providers and have weekly clinics. The investigator team has excelled when recruiting adolescent T1D patients. There are almost 4000 pediatric patients actively followed at BDC, and we do not foresee any difficulties with recruitment.

**Detailed Study Visit Descriptions:** The study timeline for is illustrated in **Fig 10**, and details from each study visit is summarized below. Visit 1 is the screening visit and visit 2 and 3 will occur consecutively.

**Visit 1 (Screening visit):** Prescreening will be done by phone or in conjunction with a clinical diabetes visit. The full screening visit will include the consent process, history, allergies confirmed, physical exam, and screening labs (HbA1c, hemoglobin and hematocrit [H&H], serum creatinine, urine microalbumin to creatinine ratio). All females will also have a pregnancy test and detailed menstrual history. The screening visit will take approximately 2 hours.

**Visit 2, part 1:** Participants will present the evening before the study visit, or present fasting to the Pediatric CTRC in the morning, and have IV(s) placed. Fasting blood will be drawn for serum copeptin, lipids, insulin, cystatin c, creatinine, sodium, hematocrit and total protein prior to the clamp. Participants will be escorted to the Brain Imaging Center or CHC Radiology for a BOLD and ASL MRI per local protocol. BOLD MRI measurements will be performed at baseline and following administration of a small dose of furosemide (20 mg IV) via the PIV. A study physician or nurse will be responsible for the furosemide administration. Total duration of part 1 will be approximately 1.5 hours.

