**Visit 2, part 2:** Participants return to pediatric CTRC and will have their blood glucose concentrations clamped in the hyperglycemic range. Participants will also undergo iohexol and PAH clearance studies, in addition to 4-hour urine collection for album excretion rate (AER) and albumin to creatinine ratio (ACR). Upon completion of visit 2, participants will be provided with a study meal (lunch). After lunch, participants will undergo DXA scan for quantification of body composition. This concludes the study. Total duration 6 hours.

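### A fasting morning MRI does not standardise glucose in youth with type 1 diabetes, and no acute glucose value enters the Aim 2 models, so H2.1 (chiefly the ASL perfusion part) could be confounded by current glucose

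*Combined protocol and SAP*

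**What the plan says.** On the Aim 2 scan, section E (Aim 2 expected outcomes and limitations) states: "We will perform the MRI fasting in the morning to remove the effects of acute glycemic variations on RPF". The same sentence also gives hydration as a reason.

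For the clearance measurements the plan uses a different tool. The hyperglycemic clamp in section IV holds glucose at 170-190 mg/dL, with bedside readings every 10 minutes, "to remove glycemic effects on GFR and ERPF". Section E, in the text under Fig 10, lists it as a safeguard: "Control for potential confounders influencing intrarenal hemodynamic function includes: renal measures obtained during mild hyperglycemia".

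The order of events is in the Detailed Study Visit Descriptions. In Visit 2, part 1: "Fasting blood will be drawn for serum copeptin, lipids, insulin, cystatin c, creatinine, sodium, hematocrit and total protein prior to the clamp". Then: "Participants will be escorted to the Brain Imaging Center or CHC Radiology for a BOLD and ASL MRI per local protocol". Part 2 begins: "Participants return to pediatric CTRC and will have their blood glucose concentrations clamped in the hyperglycemic range".

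Section IV, study design, describes glucose handling before arrival. Participants check at home and, at 250 mg/dL or above, give "a bolus of short acting insulin using their home correction factor with a blood sugar target of 200 mg/dL". They keep their usual long-acting or pump basal insulin, and hybrid closed loops are opened.

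The Data Analysis Plan (section G) lists the Aim 2 confounders to be considered: age, sex, diabetes duration, HbA1c, blood pressure, LDL-C and FeNa. Section E adds adjustment for ERPF.

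**The concern.** The plan accepts that acute glycemia disturbs renal hemodynamics, and it clamps glucose for GFR and ERPF for that reason. For the MRI it relies on fasting. In a person without diabetes a fast brings glucose into a narrow band. In this population it need not: HbA1c may be anything below 12%, and a participant at 90 mg/dL and another at 245 mg/dL could both be scanned without correction.

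H2.1 correlates copeptin with renal perfusion and oxygenation, and both sides are measured before the clamp. Section II says vasopressin takes part in osmolality regulation, so current glucose could plausibly move copeptin as well as perfusion. A shared dependence on glucose would then appear in the H2.1 correlation.

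ASL perfusion is the most exposed. The BOLD result is reported as a pre-minus-post furosemide difference, in which a stable additive glucose effect cancels within the person. The plan provides no scan-time reading to show whether glucose was stable.

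The planned covariates do not fill the gap. HbA1c reflects chronic glycemia. ERPF is measured later, under the clamp and after furosemide, so it does not describe the state during the scan.

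**Working it through.** **1. The text side by side**

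| Item | Clearance studies (GFR, ERPF) | MRI and copeptin |
|---|---|---|
| Glycemic control | Clamp, 170-190 mg/dL | Fasting; home correction at 250 mg/dL or above |
| Glucose readings described | Every 10 minutes | Home check before arrival; 8am check, timing relative to the scan not given |
| Stated glucose window | 20 mg/dL wide | None |
| Acute glucose in the models | Held by the clamp | Not listed |

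Glucose is not in the blood panel given in section IV or in Visit 2, part 1. Section IV mentions clamping before it mentions the baseline draw, but the visit description puts the draw before the clamp. Figure 8 is not available, so the order rests on the visit descriptions.

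**2. The plan's own figures**

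Two-sided alpha of 0.05 is assumed, since sidedness is not stated.

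- Aim 2, 20 against 30 participants, 0.8 SD: z = 0.8/√(1/20 + 1/30) = 2.771; power = Φ(2.771 − 1.960) = 79.1%.
- Aim 1, r = 0.38, n = 50: z = atanh(0.38) × √47 = 2.743; power = Φ(2.743 − 1.960) = 78.3%.

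Both agree with the stated 80% to within 2 points and are not in dispute. The plan gives no power figure for the H2.1 correlation.

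**3. How large could the confounding be?**

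The documents give no correlation of glucose with copeptin, ASL perfusion or HbA1c. What follows is a range under assumptions:

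- n = 50 and no true link between copeptin and perfusion.
- Glucose correlates r with each of them, in the same direction.
- HbA1c correlates ρ with scan glucose and acts only through it.

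The formulas are:

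- Unadjusted induced correlation = r².
- Partial correlation given HbA1c = r²(1 − ρ²)/(1 − r²ρ²).
- z = atanh(correlation) × √(47 − k), where k is the number of covariates.
- P(p < 0.05) = 1 − Φ(1.96 − z) + Φ(−1.96 − z).

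Model 3 has k = 5: age, sex, HbA1c, blood pressure as one term, LDL-C.

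Worked case, r = 0.3 and ρ = 0.5: partial correlation = 0.09 × 0.75/(1 − 0.09 × 0.25) = 0.069; z = 0.448; P = 7.3%.

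| r | Unadjusted: induced correlation, P | Model 3, ρ = 0.5 | Model 3, ρ = 0.7 |
|---|---|---|---|
| 0.2 | 0.04, 5.9% | 0.03, 5.4% | 0.02, 5.2% |
| 0.3 | 0.09, 9.5% | 0.07, 7.3% | 0.05, 6.1% |
| 0.4 | 0.16, 19.8% | 0.13, 12.9% | 0.09, 8.9% |

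Simulation with 20,000 runs per case agrees: 6.0%, 9.3% and 20.3% unadjusted. Adding scan glucose to model 3 brings the rate to 4.8-5.1% in all six cases. HbA1c therefore reduces the bias without removing it. If glucose moved the two measures in opposite directions, the bias would mask a true positive association instead.

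**4. Cost of the extra term**

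The correlation detectable with 80% power is tanh(2.8016/√(47 − k)): 0.407 at k = 5 and 0.412 at k = 6. At k = 0 it is 0.387, close to the plan's 0.38.

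**The case against.** The plan does more than fast the participants. Usual basal insulin continues. Three-day diet instructions fix the macronutrient shares, and the study diet risk paragraph in section D adds frequent home monitoring and daily calls to review glucose. High morning values are corrected, participants may arrive the evening before, and the clamp section has an 8am glucose check. Together these may narrow the glucose spread, and a narrow spread pushes the effect toward nothing. Serum osmolality and sodium are also measured, so the osmolality pathway could be examined in part afterwards, although the timing of the osmolality sample is not stated. The Data Analysis Plan keeps its models small on purpose to avoid overadjustment, and the fasting sentence can be read as referring to meal-related swings only.

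Much of this stands. A reader might infer that glucose goes unchecked on the study morning, or that the question could never be examined later. The documents do not support either reading: there is a home check and an 8am in-unit check, and the scan follows a local protocol that is not reproduced. A reader might also infer that the Aim 2 contrast by hyperfiltration status is biased. Nothing here shows that; the calculation concerns the H2.1 correlation only.

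The objection does not supply a scan-time window. The 8am check is written as a clamp step, with no stated timing relative to the MRI, and neither it nor the home reading is named as an analysis variable.

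**Conclusion.** The point holds as a minor, cheaply corrected gap. Fasting does not deliver the glycemic control that the Aim 2 text claims for it, the MRI and copeptin draw precede the clamp, and HbA1c is the only glycemic term in the models. Confounding of the copeptin-perfusion correlation by current glucose is possible, chiefly for ASL.

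Its size and direction cannot be derived from the documents. In the middle assumed case the false-positive rate under model 3 is 6.1 to 7.3% against a nominal 5%; at correlations of about 0.2 or less it is negligible. It is tempting to read the 20% figure as the expected error rate. It is not: it is the unadjusted result at the top of an assumed range, with equal, same-direction correlations. Model 4 and the ERPF adjustment were not modelled.

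The conclusion rests on the visit descriptions for the order of events.

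**What to change.** 1. Record bedside glucose at the copeptin draw, at scan start and at scan end. The start and end readings also show whether glucose was steady enough to cancel in the furosemide difference.
2. Pre-specify mean scan glucose (one degree of freedom) in a sensitivity analysis of the Aim 2 models, or include it as a covariate.
3. Reword the Aim 2 sentence in section E to say that a fasting morning scan removes meal effects, and that remaining glycemic variation is measured and adjusted for.

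The cost is three bedside readings (IV access is already placed in part 1), a few case report form fields, a short amendment, and the small loss of precision shown above. No participants and no pre-scan intervention are added.

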#### **Expected outcomes and limitations:**

##### **F. Potential Benefits:**

**Evidence of Direct Benefit to Subjects:** This study is designed to learn more about the vasopressinergic system (copeptin) and how it relates to intrarenal hemodynamic function and renal energetics in early DKD in T1D. The goal is to identify strategies that can be implemented to impede the development of DKD to reduce future risk of cardiovascular morbidity and mortality. No intervention is being proposed in this study, therefore participants will not directly gain a medical benefit from participating.

Information gained by conducting this study is expected to yield novel, important findings regarding the mechanisms underlying early DKD in T1D. These data will contribute to better understanding of the role of vasopressinergic system in the development of DKD. Participants will also benefit from being in close contact

with study staff, blood sugar monitoring and learning more about their renal health. All lab and procedure results with clinical relevance obtained as part of the study will be shared with participants.

**Evidence of Benefit to Society:** The importance of the knowledge gained from this protocol is high, since DKD is very prevalent in T1D and increases the risk of death from CVD and shortens lifespan. In the United States, almost half of patients with renal failure have DKD. Despite the high prevalence and gravity of DKD in youth onset T1D, widely effective therapeutic options are lacking. Diabetes mellitus is the third most prevalent severe chronic disease of childhood. DKD remains a leading cause of morbidity and mortality, and a major risk factor for CVD in diabetes. Although data to guide care of DKD in adults with diabetes are limited, even less data exist regarding the antecedents of DKD in youth with diabetes. Yet, these antecedents of adult DKD are present in children. As DKD is one of the leading causes of death in people with diabetes and the antecedents develop in childhood, data to inform clinicians as to treatment in this high-risk population are of great public health importance. In our novel and innovative proposal, we postulate that the inappropriate vasopressin activity (elevated copeptin) results in hypermetabolism of hyperfiltration with consequent increased oxygen consumption which cannot be met with the energy inefficiency of diabetes. A better understanding of the pathophysiology underlying early DKD, including hyperfiltration, and its strong relationship with the vasopressinergic system is critical to inform development of new therapeutics. Knowledge gained from this proposal will provide new information about the intrarenal hemodynamic changes associated with hyperfiltration, and the role of elevated vasopressin in early DKD development in T1D. The investigator team is also unique in being one of the few groups skilled in performing both gold standard direct measures of GFR, RPF and advanced MRI evaluation in youth with T1D.

